### *Pediatric subjects*

The special vulnerability of children requires specific measures in the informed consent process in order to safeguard their interests and to protect them from harm. As a rule, a pediatric subject is legally unable to provide informed consent. Therefore children are dependent on their parent(s)/legal guardian to assume responsibility for their participation in the clinical trial. While children are legally incapable of giving informed consent, they nevertheless may possess the ability to assent or to dissent from participation. Out of respect for children as developing persons, children will be asked whether or not they wish to participate in the research, after having been informed about the trial in a manner that is appropriate to their intellectual and emotional capacities. They will be informed to the fullest extent possible in language and terms they are able to understand. Where appropriate, participants should assent to enroll in a trial (age of assent is to be determined by IEC/IRB or to be consistent with local legal requirements). The parent(s)/legal guardian will be responsible for the actual informed consent, while the child will be asked to assent. The following information forms (including consent/assent form) will be used by the investigational staff:

- parent / legal guardian and adolescent information sheet and consent form
- children information sheet and assent form

The way these forms are composed and used will be in accordance with local laws and regulations (e.g., the age at which adolescents are legally declared 'mature' may differ from country to country, and in case children can not write their names, drawing for example a smiley face to assent is allowed practice in some countries).

All applicable forms will be submitted for review and approval to IECs/IRBs. If local regulations allow, the investigator/trial nurse or social worker could also consider having a private session with the subject to address sensitive issues related to alcohol use, sexual activity, drug screen and any other issues as needed.

## **6.5 Privacy of Personal Data**

The processing of personal data in pursuit of this trial will be limited to those data that are reasonably necessary to investigate the efficacy, safety, quality, and utility of the investigational product(s) used in this trial. These data will be processed with adequate precautions to ensure confidentiality.

The sponsor ensures that the personal data are:

- collected for a specified and legitimate purpose;
- processed fairly and lawfully;
- credible.

Explicit consent for the processing of personal data will be obtained from the participating subjects or their legally acceptable representative prior to any processing of personal data.

The sponsor or its representatives whose responsibilities require access to personal data are obliged to keep the identity of trial subjects confidential. This confidentiality will be maintained throughout the complete data processing. Trial subjects will be entitled to request confirmation of the existence of personal data held by the sponsor and will have the right to rectify erroneous or inaccurate data.

## **7 FINANCING AND INSURANCE**

### **7.1 Financial Disclosure**

The disclosed financial interest of the investigator must be collected before enrolment of the first subject, following centre completion, and 1 year following trial completion. The investigator should promptly update this information if any relevant changes occur during this period.

Disclosable financial interests will be recorded on the Investigator Financial Disclosure Form.

Any investigator(s) added as investigational staff must complete the Investigator Financial Disclosure Form at the beginning of their participation in the trial. For any investigator(s) leaving the site prior to trial completion, an Investigator Financial Disclosure Form should be obtained at the end of their participation.

### **7.2 Indemnification**

The sponsor undertakes to indemnify and hold harmless the investigator and his/her medical staff from any claim, demand or cost arising from the activities to be carried out in compliance with the protocol, as further specified in the Clinical Trial Agreement.

### **7.3 Insurance**

Sponsor ensures that an appropriate liability insurance is available covering injuries arising from the participation of the trial subject in this trial, as further specified in the ICF/Assent and the Clinical Trial Agreement.

## **8 DATA QUALITY CONTROL/ASSURANCE**

The trial is to be monitored by the sponsor or representative.

Shortly before the trial starts, the monitor meets with the investigator and all staff involved to review the procedures regarding trial conduct and recording the data on the CRF. During the trial, the investigator shall permit the monitor to verify the progress of the trial at the centre as frequently as necessary. The investigator shall make the CRFs available, provide missing or corrected data and sign the CRFs. Key data transcribed onto the CRFs, such as the subject's sex,

date of birth, assessment dates, test results, etc., are to be reviewed against source documents. Personal information is to be treated as strictly confidential and is not to be made publicly available. Any inconsistency between source data and data recorded on the CRF is to be corrected.

After termination of data collection (see [Figure 1](#)), all visits and assessments will be performed per local standard of care and documented in the subject's medical records only. Data will no longer be recorded in the CRF.

The sponsor will ensure that appropriate Quality Control (QC) steps are included into the different clinical processes to guarantee adequate protection of the trial subjects and quality of the data.

An independent Quality Assurance (QA) department, regulatory authorities and/or IECs/IRBs may review this trial. This implies that auditors/inspectors will have the right to inspect the trial centre(s) at any time during and/or after completion of the trial and will have access to source documents, including the subject's file. By participating in this trial, investigators agree to this requirement.

For any data transfer, measures will be undertaken to protect subject data handed over against disclosure to unauthorized third parties and subject confidentiality will be maintained at all times.

## **COVID-19 APPENDIX**

### **GUIDANCE ON STUDY CONDUCT DURING THE COVID-19 PANDEMIC**

It is recognized that the Coronavirus Disease 2019 (COVID-19) pandemic may have an impact on the conduct of this clinical study due to, for example, self-isolation/quarantine by participants and study-site personnel; travel restrictions/limited access to public places, including hospitals; study site personnel being reassigned to critical tasks.

In alignment with recent health authority guidance, the sponsor is providing options for study related participant management in the event of disruption to the conduct of the study. This guidance does not supersede any local or government requirements or the clinical judgement of the investigator to protect the health and well-being of participants and site staff. If, at any time, a participant's safety is considered to be at risk, study intervention will be discontinued, and study follow-up will be conducted.

Scheduled visits that cannot be conducted in person at the study site will be performed to the extent possible remotely/virtually or delayed until such time that on-site visits can be resumed. At each contact, participants will be interviewed to collect safety data. Participants will also be questioned regarding general health status to fulfill any physical examination requirement.

Every effort should be made to adhere to protocol-specified assessments for participants on study intervention, including follow up. Modifications to protocol-required assessments may be permitted via COVID-19 Appendix after consultation with the participant, investigator, and the sponsor. Missed assessments/visits will be captured in the clinical trial management system for protocol deviations. Discontinuations of study interventions and withdrawal from the study should be documented with the prefix "COVID-19-related" in the case report form (CRF).

The sponsor will continue to monitor the conduct and progress of the clinical study, and any changes will be communicated to the sites and to the health authorities according to local guidance. If a participant has tested positive for COVID 19, the investigator should contact the sponsor's responsible medical officer to discuss plans for study intervention and follow-up. Modifications made to the study conduct as a result of the COVID-19 pandemic should be summarized in the clinical study report.

### **Drug Supply:**

- Normal study drug shipment from the Janssen depots to the sites will continue until further notice.
- Normal study drug dispensation to subject by site.
- If study treatment dispensation to subject at site might be impacted, the local sponsor team should be informed by the site. Direct-to-patient (DTP) process, when permitted by local regulations in the country, will be initiated to allow sites to ship study treatment to the subjects. Only after approval by the sponsor, the granted site may ship treatment to subjects with support of the sponsor's supply team. Where DTP shipments are deemed necessary, the process must be coordinated between the site and sponsor staff following standard DTP procedures for arranging shipment and adhering to associated approvals and documentation requirements.
- Sites are requested to send their SOPs, related to drug supply and dispensation, for sponsor approval prior to implementation.
- Where necessary upon local guidance, subjects will consent upfront before the DTP process will be implemented.
- In case of remote visits, the subject should keep used and un-used kits at home at a secure location. The subject will be requested to bring the used and un-used kits back to the site at the next on-site visit.
- There will be no central study drug return organized by the sponsor.
- Sites need to continue to assess the levels of investigational product (IP) inventory to ensure the site has enough IP to cover all patients for at least 6 months. If the inventory is not sufficient the site is to contact the site manager to organize shipment of new IP.

### **Verification and Monitoring Visits:**

- Interim monitoring visits will be replaced by remote monitoring visits until such time that on-site visits can be resumed.

### **Remote Assessment Visits:**

- Remote assessment visits may be performed until such time that on-site visits can be resumed. Site staff will be asked to collect any assessments that can be made remotely. These assessments are important for the continued evaluation of safety and efficacy as patients complete the study period. Conducting remote assessment visits enables this important data to be collected without risking patient, family, and site staff safety. As allowable per local regulations, these remote assessments can be conducted via telephone with patients in their homes. Assessments that can be completed remotely include a review of adverse events and concomitant medications. Site staff will be asked to adhere to the Time and Events Schedule outlined in the protocol, to the extent feasible, when scheduling remote assessments. Some of the assessments required in the Time and Events Schedule are not in scope for remote visits including weight and urine pregnancy test (if applicable). Drug accountability can be discussed remotely but will be confirmed at the first visit back on site. These data will be missing for patients that are unable to attend site visits.

- The relationship to COVID-19 for missing protocol-specified information/procedures will be documented in the patient source documents.
- Where necessary upon local guidance, subjects will consent upfront before remote visits will be implemented.

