## 2 FLOWCHART

### 2.1 Flowchart 1: Trial Follow-up

#### Up to and including Protocol Amendment 2:

| Type of Visit  | Baseline a | Treatment period                      |                                   |   | Follow-up visit b |
|--|-----------------------|---------------------------------------|-----------------------------------|---|------------------------------|
| Time of Visit  | Day 1                 | Every 3 months for pediatric subjects | Every 6 months for adult subjects | Final / Withdrawal visit c,i | 4 weeks after withdrawal     |
| Informed Consent/Assent g   | X                     |                                       |                                   | X j                          |                              |
| Demographic data d  | X                     |                                       |                                   |   |                              |
| Height h , Tanner staging h  | X                     |                                       |                                   | X                                       |                              |
| Weight   | X                     | X                                     | X                                 |   |                              |
| Urine pregnancy test, if applicable e   | X                     | X                                     | X                                 | X                                       |                              |
| Inclusion/exclusion criteria   | X                     |                                       |                                   |   |                              |
| Dispensation of investigational medication   | X                     | X                                     | X                                 | X j                          |                              |
| Drug accountability  |                       | X                                     | X                                 | X                                       |                              |
| Adherence Counseling   | X                     | X                                     | X                                 | X j                          |                              |

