## 2.2 Flowchart 2: Simplified Trial Follow-up

### As of Protocol Amendment 3:

| Type of Visit   | Baseline Visit a | Local Standard of Care Visit b   |
|---|-----------------------------|---|
| Informed Consent/Assent   | X c              | Refer to the Final/Withdrawal Visit in Flowchart 1: Trial Follow-up |
| Inclusion/exclusion criteria  | X                           |   |
| Dispensation of investigational medication  | X                           | X f  |
| Collection of SAEs possibly related to ETR and pregnancies d   | X                           | X   |
| Study termination e  |                             | X   |
| Note: Assessments are to be performed per local standard of care and documented in the subject's medical records only. |                             |   |

a For new subjects that roll-over from (parent) trial TMC125-C234 (IMPAACT P1090). The Baseline Visit will coincide with the last visit of the previous trial.

b The next planned visit for ongoing subjects before switching to simplified data collection as per Protocol Amendment 3 will be a Final/Withdrawal Visit. During this Final/Withdrawal Visit, the informed consent will be signed, final assessments will be carried out and recorded in the CRF, and the study medication will be dispensed as described in [Flowchart 1: Trial Follow-up](#).

c Informed assent only applicable to pediatric subjects coming from (parent) trial TMC125-C234.

d Investigators will continue to report SAEs possibly related to ETR and pregnancies to the sponsor using regular pharmacovigilance reporting.

[figure not shown]
e Study termination will be documented in the subject's medical records and recorded on a separate, paper termination disposition form to be shared with the sponsor.

f If the subject exits the trial, the last visit will be a local standard of care visit but without dispensation of investigational medication.

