For ongoing subjects, the next planned visit after approval of amendment 3 will be a Final/Withdrawal Visit ([Figure 1](#)). During this Final/Withdrawal Visit, the informed consent will be signed, final assessments will be carried out and recorded in the CRF, and the study medication will be dispensed as described in [Flowchart 1: Trial Follow-up](#). For new subjects that roll-over from (parent) trial TMC125-C234 (IMPAACT P1090) after approval of amendment 3, the next planned visit will be a Baseline Visit ([Figure 1](#)). During this Baseline Visit, the informed consent will be signed and assessments will be performed per local standard of care and documented in the subject's medical records only.

For all new and ongoing subjects, all subsequent visits and assessments will be performed per local standard of care and documented in the subject's medical records only. Investigators will continue to report SAEs possibly related to ETR and pregnancies to the sponsor using regular pharmacovigilance reporting. This information will only be entered in the company safety repository.

For all new and ongoing subjects, if the subject exits the trial, the last visit will be a local standard of care visit but without dispensation of investigational medication.

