### **5.2.2 INCLUSION CRITERIA**

Subjects who meet all of the following criteria are eligible for this trial:

1. Subjects with documented HIV-1 infection.
2. Criterion modified per Amendment 3

- 2.1. Male or female subjects, aged 2 years and older.
3. Subject has successfully completed a clinical (parent) trial with ETR sponsored by or in collaboration with Janssen Research & Development, and continues to receive benefit from the use of ETR.
4. Adult has voluntarily signed the Informed Consent Form (ICF). Pediatric subject (where appropriate, depending on age) and their parent(s) or legal representative(s) have signed the ICF/Assent voluntarily. Children will be informed about the program and asked to give assent (where appropriate, depending on age).
5. Negative urine pregnancy test for females of childbearing potential.

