## 5.4 Assessments

### 5.4.1 TIMING OF ASSESSMENTS

Subjects will rollover after completion of a previous (parent) trial sponsored by or in collaboration with Janssen Research & Development. Baseline visit will coincide with the last visit of the previous (parent) trial.

Assessments and results from the last visit of the previous (parent) trial will be used for the Baseline visit of this trial; overlapping assessments only need to be conducted once. Additional assessments not included in this protocol can be done locally at the investigator's discretion as per local standard of care.

As subjects roll over from a clinical (parent) trial, a urine pregnancy test is to be performed at the Baseline visit (females of childbearing potential only) and is repeated every 3 months (pediatric subjects) or every 6 months (adult subjects) thereafter.

If a subject is considered eligible after signing of the ICF/Assent, completion of the Baseline Form, and evaluation by the sponsor or its designee, the subject receives the investigational medication (ETR) at the Baseline visit.

It is recommended that subjects be evaluated every 3 months (pediatric subjects) or every 6 months (adult subjects) after starting ETR. A Final/Withdrawal Visit is to be performed.

The exact timing of the assessments is presented in the flowchart in Section 2.

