#### 5.4.3.1.1 Clinical Laboratory Tests

A urine pregnancy test is to be performed every 3 months (pediatric subjects) or every 6 months (adult subjects) after starting ETR (females of childbearing potential only).

After termination of data collection (see Figure 1), clinical laboratory tests will occur according to the local standard of care and documented in the subject's medical records only.

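### When a Flowchart 1 visit is held remotely, the COVID-19 Appendix drops the scheduled urine pregnancy test and names no substitute or catch-up, although etravirine may still be supplied (minor, cheap patient-safety improvement)

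*Protocol*

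**What the plan says.** **Schedule.** Flowchart 1 (Protocol Part I, 2.1) has a row "Urine pregnancy test, if applicable", marked at Baseline, at the treatment visits and at the Final/Withdrawal Visit. A footnote limits it to females of childbearing potential. Section 5.4.1 adds that the test "is repeated every 3 months (pediatric subjects) or every 6 months (adult subjects) thereafter". Inclusion criterion 5 (5.2.2) reads "Negative urine pregnancy test for females of childbearing potential". No other kind of pregnancy test is scheduled.

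**From Amendment 3.** The next planned visit for ongoing subjects is the Final/Withdrawal Visit. Consent is signed there, and "final assessments will be carried out and recorded in the CRF, and the study medication will be dispensed as described in" Flowchart 1. After data collection ends, 5.4.3.1.1 says that "clinical laboratory tests will occur according to the local standard of care". Flowchart 2 (2.2) keeps the row "Dispensation of investigational medication" but has no pregnancy-test row.

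**Remote visits.** Under Remote Assessment Visits, the COVID-19 Appendix describes some scheduled assessments as "not in scope for remote visits including weight and urine pregnancy test (if applicable", and accepts that the data will be missing for those who cannot come to the site. The same paragraph gives another item a later check: "Drug accountability can be discussed remotely but will be confirmed at the first visit back on site". The pregnancy test has no such provision.

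**Supply.** Under Drug Supply, normal site dispensing continues. If it is impaired, direct-to-patient shipment may be used where local rules permit and the sponsor approves.

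**The concern.** Section 5.2.4 calls the effect of ETR on gestation unknown, and 5.2.5 makes pregnancy a mandatory reason for withdrawal. Both protections work only once a pregnancy is known. The urine test is the one scheduled measure that can find a pregnancy the subject is unaware of or does not mention. If it is skipped while supply continues, exposure in an undetected pregnancy can last longer than the schedule intended.

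A urine test is also one of the easier assessments to move off site, and the appendix asks sites to collect whatever can be done remotely. A site that reads the specific exclusion would nevertheless reasonably not arrange the test.

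**Working it through.** The documents give no sample size, error rate or other figure to reproduce here. The check is a comparison of texts plus a short interval calculation.

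**Step 1. What a remote Flowchart 1 visit keeps and loses**

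| Element | At a remote visit | Source |
|---|---|---|
| Scheduled urine pregnancy test | Lost; no substitute or catch-up named | COVID-19 Appendix, Remote Assessment Visits |
| Collection of pregnancies with the AE data | Kept | Flowchart 1, AE row; 5.1.1 |
| Safety interview at each contact | Kept | COVID-19 Appendix, general guidance |
| Reporting within 24 hours of awareness | Kept | Part II, 1.4 |
| Contraception rules | Kept | 5.2.4 |
| Extra local tests at the investigator's discretion | Kept | 5.1.1, 5.4.1 |
| ETR supply | May continue | COVID-19 Appendix, Drug Supply |

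Only the objective test drops out.

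**Step 2. Interval between protocol tests if Amendment 3 is not yet in effect (assumption)**

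Inputs: the scheduled interval s is 3 months (pediatric) or 6 months (adult), from 5.4.1. The number k of consecutive remote treatment visits is not in the documents, so a range is shown. The visit after the remote ones is assumed to be on site and on schedule.

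Interval = s × (k + 1)

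| k | Pediatric | Adult |
|---|---|---|
| 0 (as planned) | 3 × 1 = 3 months | 6 × 1 = 6 months |
| 1 | 3 × 2 = 6 months | 6 × 2 = 12 months |
| 2 | 3 × 3 = 9 months | 6 × 3 = 18 months |

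In this setting the loss is a longer interval, because the next on-site Flowchart 1 visit carries its own test.

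**Step 3. Tests lost once Amendment 3 is in effect**

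One Flowchart 1 visit remains for an ongoing subject, the Final/Withdrawal Visit.

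- Held on site or delayed: 0 tests lost.
- Held remotely: 1 test lost.
- Later protocol-scheduled tests under Flowchart 2: 0, so the schedule does not recover the lost test.

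The maximum is therefore 1 test per subject.

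**Step 4. Which setting the appendix had in mind**

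The appendix also excludes weight. Flowchart 1 marks weight at baseline and treatment visits but not at the Final/Withdrawal Visit. This suggests that remote treatment visits were envisaged, but does not prove it, so both settings are kept.

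**The case against.** The strongest reply is that little is lost and much remains.

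- **Pregnancy is still asked about and recorded at each visit.** This stands. A reader might infer that a remote visit ends pregnancy monitoring, but the kept elements in Step 1 rule that out.
- **A test elsewhere is not forbidden.** This stands too. The general guidance asks sites to make every effort to keep to protocol assessments, leaves clinical judgement to the investigator and lets a visit be delayed instead. But a discretionary test is not a scheduled one, and the specific exclusion points sites away from it.
- **The contrast with drug accountability is weak.** Returned kits have to be reconciled at some point, whereas a missed test is superseded by the next one. That is fair for treatment visits. It does not help after a remote Final/Withdrawal Visit, which no protocol test follows.
- **A remote Final/Withdrawal Visit is a corner case.** It needs a signed consent and, in children, height and Tanner staging, so it is poorly suited to remote conduct. The appendix does not exclude it, but nothing shows that one would occur.
- **The gap is disclosed and tracked.** The reason for missing procedures goes into source documents, and missed assessments are captured as deviations. That documents the omission without detecting a pregnancy.

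A reader might also infer that a safeguard on dispensing has been lost. It has not: after the negative test at entry, the protocol does not make on-site supply depend on a test result either.

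**Conclusion.** The point holds as a minor patient-safety improvement. It is a gap in the pandemic accommodation. A reader might call it a contradiction, but the appendix openly modifies the schedule and says that data will be missing.

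The size depends on whether Amendment 3 is in effect at the site, on how many consecutive visits are remote, and on whether a Final/Withdrawal Visit is ever held remotely. The documents settle none of these. They also do not give the number of females of childbearing potential affected, which may be zero.

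No analysis is affected. SAP 7.3 lists no output of pregnancy-test results; a missed test would at most appear among the COVID-related deviations.

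**What to change.** Amend the Remote Assessment Visits section of the COVID-19 Appendix so that, for a pregnancy test due at a Flowchart 1 visit held remotely:

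1. a home urine kit or a local test is used where feasible and locally permitted, with the result reported to the site and recorded in source;
2. otherwise that one owed test is done at the first on-site visit afterwards, as already provided for drug accountability. This applies even if that visit falls under Flowchart 2, and it should be worded as a single test carried over from Flowchart 1, so that it does not become a recurring Flowchart 2 assessment.

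Weight stays out of scope. The 3- and 6-month schedule, the conditions of supply and 5.2.5 stay unchanged.

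**Cost.** One or two sentences, and one kit or local test per test due at a remote Flowchart 1 visit (at most one per subject once Amendment 3 applies). A self-read result is less controlled than a site test; the on-site catch-up avoids that. Consent and confidentiality need care, particularly for minors.
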